In order to protect the overall type I error rate for the study when incorporating the hypothesis testing of the co-primary endpoints and these key secondary endpoints into the analysis, the hierarchical testing procedure in the protocol was specified as follows.

Step 1a: Test the change from baseline in ADAS-Cog (a co-primary efficacy endpoint) comparison between the gantenerumab and placebo arms at $\alpha=0.05$.

Step 1b: Test the change from baseline in ADCS-ADL (a co-primary efficacy endpoint) comparison between the gantenerumab and placebo arms at $\alpha=0.05$.

The result of Step 1 of the testing procedure is considered statistically significant only if the p-values for both Steps 1a and 1b (i.e., both co-primary efficacy endpoints) are statistically significant at $\alpha=0.05$. If either p-value is >0.05 , the result of Step 1 is considered non-significant and no further testing will be performed.

If Step 1a and Step 1b are significant, continue testing.

Step 2: Test the time to first occurrence of clinical decline between the gantenerumab and placebo arms at $\alpha=0.05$.

If Step 2 is significant,

Step 3: Test the change from baseline in CDR-SB comparison between the gantenerumab and placebo arms at $\alpha=0.05$.

If Step 3 is significant,

Step 4: Test in ADAS-Cog responder comparison between the gantenerumab and placebo arms at $\alpha=0.05$.

Safety Analyses

The safety analysis population will include all randomized patients who received at least one dose of study drug, with patients grouped according to the treatment actually received.

The following safety outcome measures will be summarized using descriptive statistics:

- Incidence and nature of MRI safety findings: ARIA-E and ARIA-H
- Incidence, nature, and severity of serious adverse events
- Incidence, nature, and severity of adverse events
 - Adverse events will be summarized by preferred term.
- Incidence of treatment discontinuations because of adverse events
- Mean changes in clinical laboratory tests from baseline over time and incidence of treatment-emergent abnormal laboratory values and abnormal laboratory values reported as adverse events
- Mean changes in ECG assessments from baseline over time and incidence of abnormal ECG assessments
- Incidence of anti-gantenerumab antibodies
- Physical and neurologic examination abnormalities

- Mean changes in vital signs assessment from baseline over time and incidence of abnormal vital sign measurements
- Changes in Columbia–Suicide Severity Rating Scale scores from baseline over time

Pharmacokinetic Analyses

Non-linear mixed-effects modeling will be used to analyze the dose concentration–time data of gantenerumab. Information from other studies in humans may be incorporated to establish the PK model. The selection of parameters and the derivation of individual measures of exposure, such as $AUC_{0-\tau}$, C_{max} , and C_{trough} , will depend on the final PK model used for this analysis. All PK parameters will be presented by listings and descriptive summary statistics, including the arithmetic mean (for $AUC_{0-\tau}$, C_{max} , and C_{trough}), median, range, SD, and CV. Details of the mixed-effects modeling analysis will be described in the Modeling and Simulation Analysis Plan and results of this analysis will be reported separately. The influence of background medication on the pharmacokinetics of gantenerumab will be explored and, if appropriate, concentration–effect relationships may be assessed post hoc for PD, efficacy, or safety measures.

Exploratory Analyses

An analysis will be performed to explore association of the treatment effect with patient genotypes to assess the influence of the APOE $\epsilon 4$ status and Fc γ receptor genotypes on the gantenerumab treatment effect, the primary efficacy variable, and selected safety parameters and summarized by each of the genotypes. Inferential statistics may be applied in case the difference is clinically relevant.

Determination of Sample Size

The purpose of this study was to test the treatment effect of gantenerumab relative to placebo. Point and interval estimates of the true treatment difference were to be presented.

A target sample size of 500 patients per arm was to be enrolled into the study. With this sample size, and based on the assumptions listed below, the study was estimated to have at least 80% power at a two-sided α level of 0.05 for testing the hypotheses of each of the co-primary efficacy endpoints using the MMRM analysis.

- Expected difference between treatment arms in the absolute change from baseline at Week 104 in ADAS-Cog13 of approximately 2.3 points, with a SD of 10.4
- Expected difference between treatment arms in the absolute change from baseline at Week 104 in ADCS-ADL of approximately 2.5 points, with a SD of 10.9
- Expected withdrawal rate (including censoring from the efficacy analysis owing to changes in medications) of approximately 30%

Subgroup Analyses

Since this is a global study, the effect of some demographic variables and baseline characteristic such as race and region on results of selected efficacy and safety variables will be summarized within subgroups using descriptive statistics (please see subgroups below). Additional exploratory analyses of efficacy results may be performed using an MMRM model, with the subgroup, a treatment-by-subgroup interaction term, and a subgroup-by-time interaction terms included along with the independent effects described above. This exploratory subgroup analysis may be important in understanding the effect of these variables on efficacy and safety. Such exploratory analyses will be performed primarily in the case where the descriptive statistics results indicate substantial differences between the subgroups.

The following variables will be used to define the subgroups for these analyses:

- Sex
- Age
- Race
- APOE $\epsilon 4$ status
- Fc γ receptor genotype
- Region

Additional subgroup analyses may be performed with subgroups defined based on baseline levels of CSF t-tau, p-tau, t-tau to A β 1–42 ratio, and p-tau to A β 1–42 ratio.

Since Part 1 (i.e., the double-blind period) has been suspended and replaced by an OLE, the primary and key secondary efficacy analyses will not be performed. However, exploratory and descriptive analyses will be conducted at the end of the study.

Interim Analyses

An interim analysis for futility was originally scheduled when approximately 50% of patients had completed 104 weeks of the double-blind treatment period. If at the time of the interim analysis, the tests of the co-primary endpoints indicated that the predictive probability of success was < 10%, then the trial may be terminated for futility.

This interim analysis was to be conducted by an independent Data Coordinating Center and will be reviewed by the independent Data Monitoring Committee.

There is no interim analysis scheduled for the OLE. However, the Sponsor will review the data on an ongoing basis.

LIST OF ABBREVIATIONS AND DEFINITIONS OF TERMS

Abbreviation	Definition
A β	amyloid-beta
AD	Alzheimer's disease
ADA	anti-drug antibody
ADAS-Cog	Alzheimer's Disease Activity Scale–Cognitive
ADCS-ADL	Alzheimer's Disease Cooperative Study–Activities of Daily Living
ADL	activities of daily living
ADNI	Alzheimer's Disease Neuroimaging Initiative
ADRDA	Alzheimer's Disease and Related Disorders Association
APA	American Psychiatric Association
APOE	apolipoprotein E
ARIA	amyloid-related imaging abnormality
ARIA-E	amyloid-related imaging abnormality–edema/effusion
ARIA-H	amyloid-related imaging abnormality–hemosiderin depositions
AUC	area under the concentration–time curve
BGTS	Barkhof Grand Total Score
BOLD	blood oxygenation level–dependent
BP	blood pressure
CDR	Clinical Dementia Rating
CDR-GS	Clinical Dementia Rating–Global score
CDR-SB	Clinical Dementia Rating–Sum of Boxes
ChEI	cholinesterase inhibitor
CHMP	Committee for Medicinal Products for Human Use
CL	Clearance
C _{max}	maximum plasma concentration
CSF	cerebral spinal fluid
C-SSRS	Columbia–Suicide Severity Rating Scale
CV	coefficient of variation
DRB	data review board
DS	Dependence Scale
DSM-5	Diagnostic and Statistical Manual of Mental Disorders, Version 5
EC	Ethics Committee
EEA	European Economic Areas
eCRF	electronic Case Report Form
EDC	electronic data capture
EMA	European Medicines Agency
F γ	Fc gamma
FDA	U.S. Food and Drug Administration

Abbreviation	Definition
FLAIR	fluid attenuated inversion recovery
fMRI	functional magnetic resonance imaging
GAS	Goal Attainment Scaling
GDS	Geriatric Deterioration Scale
HbA _{1c}	hemoglobin A _{1c}
HCLF	high concentration liquid formulation
HIPAA	U.S. Health Insurance Portability and Accountability Act
IADL	Instrumental Activities of Daily Living
ICF	Informed Consent Form
ICH	International Conference on Harmonisation
iDMC	independent Data Monitoring Committee
IEC	Independent Ethics Committee
IMC	internal monitoring committee
IMP	investigational medicinal product
iMRI-C	independent MRI committee
IND	Investigational New Drug
IRB	Institutional Review Board
ITT	intent to treat
IxRS	voice/web response system
IV	Intravenous
LAR	legally authorized representative
LPLV	last patient, last visit
MAD	multiple ascending dose
MMRM	mixed-effects model repeated measures
MMSE	Mini Mental State Examination
MRI	magnetic resonance imaging
NCD	neurocognitive disorder
NINCDS	National Institute of Neurological and Communicative Disorders and Stroke
NPI	Neuropsychiatric Inventory
OFV	objective function value
OLE	open-label extension
PD	pharmacodynamic
PET	positron emission tomography
PK	pharmacokinetic
PRO	patient-reported outcome
p-tau	phosphorylated tau
q4w	every 4 weeks
QoL	quality of life

Abbreviation	Definition
qRT-PCR	quantitative reverse transcription polymerase chain reaction
RCR	Roche Clinical Repository
rs-fMRI	resting state functional magnetic resonance imaging
RUD-Lite	Resource Utilization Dementia–Lite
SC	subcutaneous
SD	standard deviation
SUVr	standardized uptake value ratio
T	Tesla
T _{max}	time to peak concentration
t-tau	total tau
ULN	upper limit of normal
VPC	visual predictive check
ZCI-AD	Zarit Caregiver Interview for Alzheimer's Disease

1. **BACKGROUND**

1.1 **BACKGROUND ON ALZHEIMER'S DISEASE**

According to the figures provided by Alzheimer's Association in 2015, an estimated 47 million people worldwide are living with dementia, with the number projected to 76 million cases in 2030. Alzheimer's disease (AD) is the most common cause of dementia, accounting for 60%-80% cases. In the United States, it is the sixth leading cause of death, and the rate has increased by 71% from 2000 to 2013 (Alzheimer's Association 2015).

AD is clinically characterized by a progressive impairment in cognitive and executive abilities, which results in decreased function and gradual loss of independence (Mesterton et al. 2010). Although the course of illness will vary from patient to patient, in general, the clinical picture evolves from "predementia/prodromal AD" to mild, moderate, and severe AD. The progressive decline that starts in the predementia stage of AD initially presents as an impairment of memory, language, and visuospatial function, some of which can be explained by loss of cholinergic neurons in the basal forebrain. This neuronal loss contributes to the symptom development of AD. As AD advances, patients become progressively impaired and the burden on caregivers significantly increases. Because of its increasing prevalence, long duration, and high cost of care, AD is expected to continue to represent a major public health problem for decades to come.

The main pharmacologic approach to treatment aimed at limiting cognitive and functional decline in AD is to increase synaptic levels of acetylcholine through use of cholinesterase inhibitors (ChEIs). Currently available ChEIs include donepezil (Aricept[®]), galantamine (Reminyl[®]/Razadyne[®]), rivastigmine (Exelon[®]), and tacrine (Cognex[®]). Accumulating data have demonstrated that current pharmacotherapy provides limited symptomatic benefit; ChEIs can provide an improvement in cognitive function for 6–18 months followed by deterioration along a parallel path (Neugroschl and Sano 2010), whereas memantine (Namenda[®]) provides only modest improvement in global measures of functioning both with and without a ChEI (Neugroschl and Sano 2010). These medications have no effect on the progressing neuropathology (Gauthier et al. 2006; Hsiung and Feldman 2008; Schneider et al. 2011) and do not significantly change the course of the illness (Neugroschl and Sano 2010).

Increasingly, drug discovery and development in AD are focused on disease-modifying treatments that target amyloid-beta (A β) peptide, tauopathies, and other pathologic consequences of AD. Modifying the course of AD could lead to significant public health benefits. For example, an intervention that could delay the onset of AD by 2 years could potentially decrease the incidence in such a way that in 50 years there would be nearly 2 million fewer cases than are currently projected (Neugroschl and Sano 2010).

The amyloid hypothesis is currently the most influential concept in the pathogenesis of AD and a powerful driver of drug development (Kurz and Pernecky 2011). According to the amyloid hypothesis, accumulation of A β in the brain is the primary factor driving AD pathogenesis (Selkoe 1991; Hardy and Selkoe 2002; Selkoe et al. 2012). The rest of the disease process, including tau phosphorylation and formation of neurofibrillary tangles, results from an imbalance between production and clearance of A β (Selkoe 1991; Hardy and Selkoe 2002). This imbalance is caused by overproduction of A β and by impaired clearance of A β from the brain. In addition to defective clearance of A β as a result of normal aging (Kress et al. 2014), reduced clearance can be caused by increased aggregation, defective degradation, disturbed balance of transport across the blood–brain barrier, or inefficient peripheral removal of the peptide (Kurz and Pernecky 2011). Accumulating evidence has suggested that monoclonal anti-A β antibodies can bind to A β and promote its clearance (Salloway et al. 2009; Ostrowitzki et al. 2012), thus potentially reducing deposition of A β aggregates, reducing neurodegeneration, and slowing progression of AD. Additional evidence comes from recent findings on aducanumab (Biogen Idec), a high affinity, fully human IgG1 monoclonal antibody that targets fibrillar and oligomeric forms of A β through microglia-mediated clearance of amyloid plaques (Hang et al. 2015). Specifically, results from an interim analysis of the Phase Ib study of aducanumab (BIIB037; PRIME study) on a total of 166 patients (placebo [n=40], 1 mg/kg [n=31], 3 mg/kg [n=33], 6 mg/kg [n=30], and 10 mg/kg [n=32]) with prodromal or mild AD, showed a dose- and time-dependent reduction of amyloid plaque in the brain that was associated with a beneficial clinical effect (Sevigny et al. 2015).

1.2 DIAGNOSTIC AND STATISTICAL MANUAL OF MENTAL DISORDERS, VERSION 5: MAJOR NEUROCOGNITIVE DISORDER DUE TO ALZHEIMER'S DISEASE

The Diagnostic and Statistical Manual of Mental Disorders, Version 5 (DSM-5; American Psychiatric Association [APA] 2013) formalizes a two-step method of diagnosis; first, a diagnosis of cognitive impairment is made, and then the underlying etiology is determined (APA 2013).

The DSM-5 does not use the term “Alzheimer’s disease” alone as a diagnosis. The DSM-5 also replaces the term “dementia” with the term “major or mild neurocognitive disorder” (NCD; APA 2013). As such, mild AD is now referred to as major NCD due to AD, mild severity (APA 2013). Patients diagnosed with major NCD due to AD, mild severity have impairments in one or more cognitive domains, with progressive, gradual declines in learning and memory, intact instrumental activities of daily living (IADL), and evidence of no other etiologies.

This protocol will refer to the clinical diagnosis of AD according to the DSM-5 (i.e., as NCD due to AD, mild severity), which is consistent with the National Institute of Neurological and Communicative Disorders and Stroke/Alzheimer’s Disease and

Related Disorders Association (NINCDS/ADRDA) criteria for mild severity (McKhann et al. 1984) and thus the protocol will use mild AD throughout.

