4.5.6.6 Columbia–Suicide Severity Rating Scale

The C-SSRS (<http://www.cssrs.columbia.edu>) is an assessment tool used to assess the lifetime suicidality of a patient (C-SSRS at baseline) as well as any new instances of suicidality (C-SSRS since last visit). The structured interview prompts recollection of suicidal ideation, including the intensity of the ideation, behavior, and attempts with actual/potential lethality. The C-SSRS baseline will be collected at baseline and the C-SSRS since last visit will be collected at subsequent visits.

The C-SSRS will be conducted at visits, as indicated in the schedule of assessments. The assessment will be completed by a certified C-SSRS rater after interviewing the patient and the patient's caregiver when in attendance at the visit.

During the OLE, the C-SSRS will be collected every 6 months. Additional C-SSRS may be collected as deemed necessary by the Principal Investigator.

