6.1.4 Safety Analyses

The safety analysis population will include all randomized patients who received at least one dose of study drug, with patients grouped according to the treatment actually received.

The following safety outcome measures will be summarized using descriptive statistics:

- Incidence and nature of MRI safety findings: ARIA-E and ARIA-H
- Incidence, nature, and severity of serious adverse events

- Incidence, nature, and severity of adverse events
Adverse events will be summarized by preferred term.
- Incidence of treatment discontinuations because of adverse events
- Mean changes in clinical laboratory tests from baseline over time and incidence of treatment-emergent abnormal laboratory values.
- Mean changes in ECG assessments from baseline over time and incidence of abnormal ECG assessments
- Incidence of anti-gantenerumab antibodies
- Physical and neurologic examination abnormalities
- Mean changes in vital signs assessment from baseline over time and incidence of abnormal vital sign measurements
- Changes in C-SSRS scores from baseline over time

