1. BACKGROUND

This document describes the statistical data that will be reported in the Clinical Study Report (CSR) for double blind treatment (Part 1) of Study WN28745 and will focus on the statistical methodology underlying the report. The efficacy and safety endpoints that will be the basis for comparing treatments will be defined in full in this document along with the populations of patients that are to be used in the analyses.

Dosing in study WN25203, investigating gantenerumab in prodromal Alzheimer's Disease (AD), was stopped in December 2014 due to a futility analysis. Consequently, recruitment into study WN28745 was stopped early. The final patient was randomized into study WN28745 on the 9th December 2015. Patients active in study WN28745 continued to receive study treatment until they discontinued from the study, finished the study, or transferred into the open label extension (OLE).

Although there will be reporting of study data in a variety of contexts beyond that of the CSR, such as the independent Data Monitoring Committee (iDMC), this document will not cover those contexts.

The description of layouts for the CSR outputs, the details about the underlying analysis datasets and programs, and the linking of production outputs to sections in the CSR are not within the scope of this document and will be covered in separate documents.

The language used in this statistical analysis plan (SAP) supersedes that in the protocol and protocol synopsis.

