2.3.4 Safety Outcome Measures

- Incidence and nature of MRI safety findings: ARIA-E and ARIA-H
- Incidence, nature, and severity of serious adverse events
- Incidence, nature, and severity of adverse events
- Incidence of treatment discontinuations due to adverse events
- Mean changes in clinical laboratory tests from baseline over time and incidence of abnormal laboratory values and abnormal laboratory values reported as adverse events
- Mean changes in ECG assessments from baseline over time and incidence of abnormal ECG assessments
- Incidence of anti-gantenerumab antibodies
- Physical and examination abnormalities
- Mean change in vital signs assessment from baseline over time and incidence of abnormal vital signs measurements

- Suicidal ideation, suicidal behavior, and self-injurious behavior without suicidal intent, as determined using the Columbia–Suicide Severity Rating Scale (C-SSRS)

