4.5 SAFETY ANALYSES

Descriptive statistics will be used to analyze all safety data. The outputs defined in this section will be produced using the safety analysis population, unless otherwise specified.

For all safety analyses, Day 1 will be defined as the start date of double-blind randomized treatment.

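### Part 1 C-SSRS is specified only as change from baseline, which sets a lifetime form against since-last-visit forms, and the Part 1 SAP gives no analysis to replace it

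*Protocol*

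**What the plan says.** **Analysis.** The safety list in the Protocol synopsis includes "Changes in Columbia–Suicide Severity Rating Scale scores from baseline over time", and Protocol 6.1.4 repeats it as "Changes in C-SSRS scores from baseline over time". Neither place gives any further C-SSRS method.

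**Instrument.** Protocol 4.5.6.6 says the scale is used to "assess the lifetime suicidality of a patient (C-SSRS at baseline) as well as any new instances of suicidality (C-SSRS since last visit"). The same section fixes which form is used when: "The C-SSRS baseline will be collected at baseline and the C-SSRS since last visit will be collected at subsequent visits". In Protocol Appendix 1 the C-SSRS is done on Day 1 and then at each 4-weekly dosing visit.

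**Part 1 SAP.** It opens by saying "The language used in this statistical analysis plan (SAP) supersedes that in the protocol and protocol synopsis". Section 2.3.4 lists the three C-SSRS categories (ideation, behaviour, self-injury without intent) as a safety outcome, much as Protocol 3.5.4 does. Section 4 defines baseline, for all analyses, as the last assessment up to and including the first dosing day; for the C-SSRS that is the lifetime form. Section 4.5 says "Descriptive statistics will be used to analyze all safety data". Its subsections 4.5.1 to 4.5.8 then cover exposure, adverse events, MRI and injection-site findings, laboratory data, vital signs, ECG, deaths and subgroups. None covers the C-SSRS.

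**OLE SAP.** Section 5.7.7 summarises the three categories at each visit, by previous randomisation and overall, with no change from baseline.

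**The concern.** A change from baseline needs the same quantity measured twice. Here the first measurement spans a lifetime and each later one spans about four weeks. A patient with past ideation and no new event appears to improve. A patient with past severe ideation and new, milder ideation also appears to improve, or at best appears unchanged.

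Suicidality is a named safety outcome, and Part 1 is the only part with a placebo control. If the protocol bullet is followed, each arm's table can show a reassuring fall that comes from the forms alone, and some new events will not be visible as worsening in that table.

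**Working it through.** The documents give no C-SSRS rate, so there is no planned figure to reproduce. The check is first textual and then an illustration with assumed rates.

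**1. Which rule governs Part 1**

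| Source | What it gives for the C-SSRS |
|---|---|
| Protocol synopsis and 6.1.4 | Change in scores from baseline over time |
| Protocol 3.5.4 | The three categories as an outcome; no method |
| Part 1 SAP 2.3.4 | The same categories as an outcome; no method |
| Part 1 SAP 4.5 | Descriptive statistics for safety in general; no C-SSRS subsection |
| OLE SAP 5.7.7 | The three categories summarised by visit (Part 2 only) |

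The SAP supersedes the protocol where it says something different. Its outcome list only repeats one that already stands in the protocol alongside the change bullet, so it does not withdraw that bullet.

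**2. Can past history be present?** Yes. Protocol 4.1.2.1 excludes patients whom the investigator judges to be at risk of suicide; it does not exclude a lifetime history. Protocol 4.1.2.8 permits stable maintenance treatment for mood disorders.

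**3. Within-arm change.** Take a yes/no indicator of any suicidality. Let p be the share positive on the lifetime form and q the share positive on a since-last-visit form. Mean change = q - p. Assumed values give, in percentage points:

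| p | q = 0% | q = 1% | q = 3% |
|---|---|---|---|
| 5% | -5 | -4 | -2 |
| 10% | -10 | -9 | -7 |
| 20% | -20 | -19 | -17 |

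The sign is negative whenever p exceeds q.

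**4. New events that need not show as worsening.** On the indicator, a patient with a history and a new event scores 1 - 1 = 0. The share of new cases arising in such patients is p·RR / (p·RR + 1 - p), where RR is the risk of a new event with a history relative to none.

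- RR = 1: 5% to 20% for p = 5% to 20%.
- RR = 5: 0.25/(0.25 + 0.95) = 21% at p = 5%; 1.0/(1.0 + 0.8) = 56% at p = 20%.

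On a graded severity scale these are upper limits, because a new event worse than the lifetime worst would still show.

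**5. Between-arm difference in expectation.** With equal p in both arms, (q1 - p) - (q0 - p) = q1 - q0. For q1 = 3% and q0 = 1% this is 2 points at p = 5% and also at p = 20%. There is no bias.

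**6. Noise in the between-arm difference.** The Protocol synopsis gives 389 enrolled in Part 1, so about 195 per arm.

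- Counting new cases directly at q = 1%: SE = √(2 × 0.01 × 0.99/195) = 1.0 point.
- The baseline difference alone: √(2 × 0.05 × 0.95/195) = 2.2 points at p = 5%; √(2 × 0.20 × 0.80/195) = 4.1 points at p = 20%.
- Variance ratio, change score to direct count, with p and q independent: (0.0475 + 0.0099)/0.0099 = 5.8 at p = 5%; (0.16 + 0.0099)/0.0099 = 17.2 at p = 20%.
- Opposite extreme, with every new event in a patient with a history: the covariance is q(1 - p), and the ratio is (0.0574 - 0.019)/0.0099 = 3.9 at p = 5% and (0.1699 - 0.016)/0.0099 = 15.5 at p = 20%.

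Under these assumptions, subtracting the lifetime record multiplies the variance roughly 4- to 17-fold and returns no information about new events.

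**The case against.** **No subtraction is written down.** The neighbouring protocol bullets for laboratory, ECG and vital signs speak of mean changes; the C-SSRS bullet does not. No document defines a numeric C-SSRS total, and a categorical shift table could satisfy the wording. This stands in part: the arithmetic in the working is one reading of the bullet. But any display that presents later status as a change from the Day 1 form compares unequal windows. A shift table is sound only if the lifetime column is labelled as history and the later column is the worst category after first dose, and nothing in the plan says so.

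**The SAP governs, and it lists categories.** True, and table layouts are left to other documents. But a list of outcomes is not an analysis, and 4.5 spells one out for the laboratory, vital-sign and ECG outcomes in the same list.

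**The placebo arm carries the same artefact.** This stands for expectation. A reader might infer that the treatment comparison is biased; the documents do not support that, because allocation was randomised 1:1 and both arms use the same forms. What remains is the misleading within-arm figure and the added noise.

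**Other channels exist.** Adverse events are sought at every patient contact (Protocol 5.3.1) and tabulated with patient-year rates (Part 1 SAP 4.5.2), deaths are listed, and an unblinded iDMC reviewed safety. This also stands: it would be wrong to conclude that new suicidality would go unseen in the trial. The defect is in the C-SSRS table.

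**Part 2.** Protocol 6.2 refers Part 2 safety analyses to 6.1.4, so a reader might infer that the OLE inherits the rule. It does not: the OLE SAP states that it supersedes the protocol and gives its own by-visit summary. The OLE baseline would also normally be a since-last-visit form.

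**Conclusion.** The point holds for Part 1. The only specific C-SSRS analysis compares a lifetime record with records of about four weeks, and the Part 1 SAP names the outcome without supplying a replacement. Within-arm change is biased toward improvement whenever lifetime prevalence exceeds the per-visit rate, and new events no worse than the lifetime worst do not appear as worsening. The arm difference is unbiased in expectation if history is balanced, but noisier than a direct count.

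The direction follows from the documents. The size does not: the -2 to -20 points, the 5% to 56% of new cases and the 4- to 17-fold variance all rest on assumed rates, and the first and last also on treating the bullet as a subtraction. The exclusion of patients judged at risk of suicide or with a raised depression score may make the true rates lower.

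**What to change.** In Part 1 SAP 4.5, add a C-SSRS subsection that:

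- reports, by arm, the number and percentage of patients with any suicidal ideation after first dose (worst category reached), any suicidal behaviour, and any self-injurious behaviour without suicidal intent;
- uses the lifetime baseline form only to classify history, for example in a shift table of worst post-baseline category against lifetime category;
- states that this replaces the change-from-baseline bullet in the Protocol synopsis and 6.1.4.

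Rates per patient-year, which the SAP already uses for adverse events, are optional. Part 2 needs no change.

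The cost is a paragraph of SAP text and one or two tables from data already collected. No new assessments are needed.
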